Main objective and primary endpoint	To compare the effect hydrocortisone plus fludrocortisone vs. placebo on a composite of death or persistent organ dysfunction – defined as continued dependency on mechanical ventilation, new renal replacement therapy, or vasopressors – assessed at 90 days on intensive care unit (ICU) adults and having different biological profiles for immune responses and corticosteroids bioactivity The primary endpoint is death or persistent organ dysfunction (defined as continued dependency on mechanical ventilation, renal replacement therapy, or vasopressors) and with SOFA score >6 up to 90 days.						
Secondary objectives	 Mortality and health-related quality of life at 6 months; 						
and endpoints	 Daily organ function (SOFA score days 1, 2, 3, 4, 7, 10, 14, 28, and 90); 						
	 Daily secondary infections (up to 90 days) Daily blood and urinary levels of glucose, sodium and potassium (up to 28 day) Daily gastroduodenal bleeding (up to 28 day) Daily cognitive function and muscles' strength (days 1 to 28, 90 and 180 days) 						
Study design	Multi-arms Parallel blinded randomized controlled trial preceded						
	by a 6-month run-in observational period. Observational phase (run-in period) Interventional phase. 						
Inclusion Criteria	1. Patients ≥18 years old;						
observational phase: (N°1,2,3,4,6,7,8,9) interventional phase:	 Admitted to ICU with proven or suspected infection as the main diagnosis; Community acquired pneumonia related sepsis OR vasopressors dependency (norepinephrine, epinephrine, vasopressin, dopamine, phenylephrine) OR septic shock (Singer 2016: vasopressor to maintain mean blood pressure of at least 65 mmHg and lactate levels above 2 mmol/l) OR acute 						
(N°1,2,3,4,5,6,7,8).	 respiratory distress syndrome (ARDS – Ranieri 2012: a- acute onset, i.e. within one week of an apparent clinical insult and with progression of respiratory syndrome, b- bilateral opacities on chest imaging not explained by other pulmonary pathologies, e.g. pleural effusion, atelectasis, nodules etc, c-no evidence for heart failure or volume overload, d- PaO2/FiO2 ≤ 300 mm Hg, - PEEP ≥ 5 cm H2O Patient who has signed an informed and written consent whevener he/she is able of consent, if not, if not ascent from his/her representant whenever he/she is present at time of screening for inclusion 						

	5. Patients who have been tested for one or more RECORDS
	specific biomarkers:
	a. CIRCI
	b. Endocan
	c. GILZ
	d. CPD

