1.4.2 The challenge of corticosteroids responsiveness in sepsis

The crude absolute reduction in mortality in these two trials was about 6.5%. It is likely that among the heterogeneous population of sepsis, some patients may draw much substantial survival benefit whereas others may be harmed. Corticosteroids survival benefit is not affected by age, gender, disease severity, type of infection, source of infection, or type of pathogens (Lamontagne 2018). There is currently no diagnostic test for CS sensitivity/resistance in sepsis. The scientific community is competing to identify markers delineating between patients who draw survival benefit from corticosteroids (CS-sensitive sepsis) and those who may be harmed (CS-resistant sepsis). In sepsis, the deregulated response may result in systemic inflammation and organs damage, or immune paresis and secondary infections (van der Poll 2017). Obviously, patients with systemic inflammation may benefit from CS whereas those with immune paresis may deteriorate. We looked for an interaction between survival in response to corticosteroids and the presence of CIRCI according to the ACTH test results (cortisol increment of less than 9 μ g/dL). The benefits from corticosteroids were more important in patients with CIRCI in the Ger-Inf-05 trial but not in

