5.14.2 Secondary Outcomes

The secondary outcomes will include:

1) Mortality at 7, 14, 28 day and 6 months.

2) Vasopressor free days: defined as the number of days with permanent hemodynamic stability in the absence of any vasopressor agent, norepinephrine, phenylephrine, epinephrine, dopamine, vasopressine or its analogs, and soever. When a patient will die on vasopressor therapy, the corresponding vasopressor free day will be 0.

3) Mechanical ventilation free days: defined as the number of days with permanent appropriate oxygenation while the patients is extubated and breathing spontaneously, i.e. no need for non invasive ventilation, high flow oxygen or CPAP. Other uses of non-invasive ventilation (e.g., chronic night-time use for chronic obstructive pulmonary disease) are not counted. When a patient will die on mechanical ventilation or will be discharge home on mechanical ventilation, the corresponding mechanical ventilation free day will be 0.

4) Organ dysfunction free days: Organ function (including renal function) will be assessed by the SOFA score (Vincent 1996). Organ dysfunction will be defined by a SOFA score of > 6 (Annane 2018). Organ dysfunction free days are defined by the number of days with os total SOFA score of 6 or less. When a patient will die on vasopressor therapy, the corresponding vasopressor free day will be 0.

5) HRQoL in 6-month survivors assessed by the EuroQol-5D (EQ-5D). This questionnaire is a standardised measure of health status developed to provide a simple, generic measure of health for clinical and economic appraisal. It is made up for two components; health state description and evaluation. The health status is measured in terms of five dimensions; mobility, self-care, usual activities, pain/discomfort, and anxiety/depression. In evaluation part, the respondents evaluate their overall health status using the visual analogue scale. See Figure 4.

6) Proportion of patients with a decision to withhold and/or withdraw active treatments

7) ICU and hospital length of stay

8) Rate of re-admission to the ICU during the 180 days after randomization

9) Safety endpoints:

- Proportion of patients affected by any serious adverse events associated with corticosteroids, among the following: hospital-acquired infections, hyperglycemia, hypernatremia, neurological disorders (coma, stroke or muscle weakness, as defined below) during the 90 days after randomization
- Coma will be defined as a Glasgow coma score < 8

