9 STATISTICAL ANALYSIS

9.1 SAMPLE SIZE DETERMINATION

We will enroll a total of at most 1800 patients. Sites are expected to enroll at least 1 or 2 patients per month.

Adaptive outcomes

The goal is to develop an adaptive clinical trial design which evaluates the therapeutic intervention of targeted therapy, identifies subset of subjects who respond better to the experimental therapy.

Sequential analyses will use the number of vasopressor-free days at day 28 as the measure of efficacy, and the occurrence of severe adverse events within the first 28 days as the measure of toxicity. According to the literature (the APPROCCHS trial), the number of vasopressor-free days at day 28 in the hydrocortisone+fludrocortisone group was 17.1 ± 10.8 versus 15.0 ± 11.1 in the placebo group. Thus, a sample of 176x2=352 patients achieves 80.04 % power to reject the null hypothesis of equal means when the mean difference between arms is 3 days with SD of 10 days, and with a significant level (alpha) of 0.05 using a two-sample t-test. For interactions to be detected with the same power as the overall effect, sample sizes should be inflated (Brookes 2004); estimated here at a multiple of fourfold; therefore, to handle potential dropouts, a sample of 1800 patients was considered to be enrolled.

Note that Bayesian inference will be used for sequential analyses, so that no inflation of type I error rate is to be corrected.

Primary outcome

To detect a 10% absolute risk reduction (from 45% to 35%) in the day 90 mortality, a sample size of 373 evaluable patients per arm (thus a total of 746 patients) is required to reach a 80% power. The planned sample of 1800 patients will achieve a 99.16%

power to reject the null hypothesis of equal mortality when the difference between arms is 10% overall, and with a 5% alpha level.

Sample sizes were computed using PASS 15 software (2017).

The power to detect this difference within each group of analysis will depend on the prevalence of each biomarker of interest.

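### Six-month EQ-5D is compared between arms in survivors only, so any mortality effect could bias it, in either direction and unequally across biomarker cohorts; an analysis that includes deaths should be added

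*Protocol*

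**What the plan says.** Item 5 of Protocol section 5.14.2 sets the population as well as the instrument: "HRQoL in 6-month survivors assessed by the EuroQol-5D (EQ-5D"). Section 2.2, whose heading applies to each analysis by biological marker, lists 6-month HRQoL among the effects to be compared between hydrocortisone plus fludrocortisone and placebo, without restricting it to survivors. The study summary pairs the two outcomes as "Mortality and health-related quality of life at 6 months", but section 5.14.2 keeps mortality as a separate item: "Mortality at 7, 14, 28 day and 6 months".

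No rule brings deaths into the HRQoL outcome. The same list does have such rules for the vasopressor-free and ventilation-free days, for example "When a patient will die on vasopressor therapy, the corresponding vasopressor free day will be 0".

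Three other places bear on the point:

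- Section 9.1 plans "To detect a 10% absolute risk reduction (from 45% to 35%) in the day 90 mortality".
- Section 4.1.3 assumes that some biomarker cohorts benefit from corticosteroids while others may be harmed.
- Section 5.16 commits to intention to treat.

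**The concern.** Being alive at 6 months is a post-randomisation event that the treatment is expected to influence. If treatment prevents deaths, the treated survivors include patients who would have died on placebo, and the placebo survivors have no counterpart to them. If those extra survivors are in worse health, the survivors-only mean falls in the treated arm although no patient was made worse. If treatment causes deaths in a cohort, the same mechanism can make it look favourable.

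The trial exists to contrast cohorts that may differ in their mortality effect. The distortion would then differ between cohorts too, and could be mistaken for a biomarker-specific effect on quality of life. The blinding cited in section 9.2.2 protects how HRQoL is assessed, not who is compared.

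**Working it through.** **Inputs from the protocol.** Mortality of 45% vs 35% at day 90 (section 9.1), a mortality reduction of about 6.5 points in earlier trials (section 1.4.2), short-term relative risks of death of 0.91 to 0.96 (section 1.4.1), and at most 1800 patients at 1:1, so 900 per arm.

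**Assumptions.** Day-90 rates carry over to 6 months. Placebo mortality is 45% in every scenario. Treatment only adds survivors. Mean EQ-5D is 0.65 in patients who survive on either arm. The extra survivors score d lower, with d from 0 (equal health) to 0.35. The protocol gives no EQ-5D values.

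**The plan's own figure.** The protocol states no figure for HRQoL. Its planning rates do reproduce its sample size: (0.45×0.55 + 0.35×0.65) × (1.960 + 0.842)² / 0.10² = 373 per arm. Power with 900 per arm comes to 99.14%, against 99.16% stated.

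**Survivors-only bias.** The extra survivors' share of treated survivors is (pC − pT)/(1 − pT), and the bias is −share × d. At 45% vs 35% with 900 per arm there are 495 placebo and 585 treated survivors. The extra 90 make up 90/585 = 15.4% of the treated survivors.

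| Mortality, placebo vs treated | Share | d = 0 | d = 0.15 | d = 0.25 | d = 0.35 |
|---|---|---|---|---|---|
| 45% vs 35% (10 points) | 0.10/0.65 = 0.154 | 0 | -0.023 | -0.038 | -0.054 |
| 45% vs 38.5% (6.5 points) | 0.065/0.615 = 0.106 | 0 | -0.016 | -0.026 | -0.037 |
| 45% vs 40.95% (relative risk 0.91) | 0.0405/0.5905 = 0.069 | 0 | -0.010 | -0.017 | -0.024 |
| 45% vs 43.2% (relative risk 0.96) | 0.018/0.568 = 0.032 | 0 | -0.005 | -0.008 | -0.011 |

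**Opposite direction.** With the first row's rates exchanged (35% placebo, 45% treated), the placebo arm holds the extra survivors. The bias is then 0 to +0.054, so a harmful treatment would look favourable.

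**Against sampling error.** Take d = 0.2 at 45% vs 35%, with an assumed EQ-5D standard deviation of 0.25 to 0.30. The bias is -0.031, with a standard error of 0.0156 to 0.0186 at 900 per arm. The chance of a nominally significant apparent harm, Φ(|bias|/SE − 1.96), is about 51% to 38%. At 373 per arm it is about 25% to 19%, and it would be lower in smaller cohorts.

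**All randomised patients, death scored 0.** At 45% vs 35% the difference is 0.10 × u, where u is the extra survivors' mean. For u = 0.30, 0.40 and 0.50 it is +0.030, +0.040 and +0.050, against -0.054, -0.038 and -0.023 among survivors.

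**What that score can hide.** At u = 0.40, a true loss of 0.040/0.55 = 0.073 in every patient who survives on either arm would bring the all-randomised difference to zero.

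**The case against.** Only living patients can answer a questionnaire, so item 5 could be read as naming who is assessed and leaving the treatment of deaths to the analysis plan, which is not shown. That stands in part: the plan may already include an analysis with deaths. It does not remove the point, because the protocol fixes a population for what it calls a comparison of arms, and an analysis plan would start from that definition.

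Six-month mortality is reported as its own outcome, so readers would have context. That lowers the priority, but a separate mortality result does not tell them how much of an HRQoL difference is selection.

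A reader might infer that a life-saving treatment will be shown to worsen quality of life, or that the sign must reverse. The documents do not support this. They give no EQ-5D values and do not say that the extra survivors are the frailest; with equal health the bias is zero. The 10-point effect is the largest available and is a day-90 figure. Section 9.1 calls it mortality under the heading of a primary outcome that section 5.14.1 defines as a composite. The protocol's own evidence on earlier trials points to smaller effects.

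A reader might also infer that the survivor outcome should simply be replaced by EQ-5D with death scored 0. That goes too far. The +0.040 in the example is the mortality effect multiplied by the extra survivors' score, and such a score could hide a real loss of 0.073 among survivors. Section 5.14.2 describes five dimensions and a visual analogue scale, but names no index or value set.

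**Conclusion.** The point holds as a weakness in how a secondary outcome is defined. The survivors-only comparison does not preserve the randomised groups once treatment affects mortality, which the trial plans for and which it expects to vary by biomarker. The bias could run in either direction. With 45% placebo mortality and extra survivors 0 to 0.35 lower, it is 0 to -0.054 at 10 points, 0 to about -0.037 at 6.5 points, and at most -0.024 to -0.011 at relative risks of 0.91 to 0.96. All of these sizes rest on assumed EQ-5D values, on the 45% rate applying at 6 months, and on treatment only adding survivors. They show what could happen and do not predict the result. Priority is modest: HRQoL enters no sample size, interim or stopping rule, and the primary conclusion is untouched.

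**What to change.** In section 5.14.2, item 5, and in the analysis plan:

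1. For the 6-month HRQoL comparison, add an analysis of all randomised patients that includes deaths. This can be a rank outcome with death as the worst value, or the EQ-5D index with death at 0 if an index and value set are named.
2. Label the survivors-only result descriptive.
3. Report both beside 6-month mortality, by arm, in each biomarker cohort.

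Vital status and HRQoL are already collected at 180 days (sections 5.5 and 5.15), so the cost is wording, one further analysis and, for the index version, the choice of a value set. The downside is that the all-randomised score partly reflects mortality and could mask a loss among survivors. For that reason the survivor summary is kept, not replaced.

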4.1.2 Interventional phase

4.1.2.1 ELIGIBILITY CRITERIA (INTERVENTIONAL PHASE)

4.1.2.1 Inclusion Criteria (interventional phase)

- 1) Patients \geq 18 years old;
- 2) Admitted to the ICU with proven or suspected infection as the main diagnosis;
 - 3) Community acquired pneumonia related sepsis OR vasopressors dependency (norepinephrine, epinephrine, vasopressin, dopamine, phenylephrine) OR septic shock (Singer 2016: vasopressor to maintain mean blood pressure of at least 65 mmHg and lactate levels above 2 mmol/l) OR acute respiratory distress syndrome (ARDS Ranieri 2012: a- acute onset, i.e. within one week of an apparent clinical insult and with progression of respiratory syndrome, b-bilateral opacities on chest imaging not explained by other pulmonary pathologies, e.g. pleural effusion, atelectasis, nodules etc, c- no evidence for heart failure or volume overload, d-PaO2/FiO2 ≤ 300 mm Hg, PEEP ≥ 5 cm H2O

4) Patient who has signed an informed and written consent whevener he/she is able of consent, if not, if not ascent from his/her representant whenever he/she is present at time of screening for inclusion

- 5) Patients who have been tested for one or more RECORDS specific biomarkers
 - o CIRCI
 - o Endocan
 - o GILZ <
 - o CPD
 - o Transcriptomic SRS2
 - o Endotype B
 - o PCR COVD-19
 - o PCR Influenza
 - o PCR other respiratory virus

6) Affiliation to a social security system or to an universal health coverage (Couverture Maladie Universelle, CMU);

7) Patients under guardianship or curatorship will be included;

8) Patients in case of simple emergency (legal definition) will be included.

RECORDS" protocol, version 4.0 of 03/03/2021

16/61

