5.12.1 Unauthorized treatments

- Hydrocortisone and other corticosteroids whatever the dose and the route (except local administration, nebulization not being considered as a local administration) are not allowed, except dexamethasone 6mg per day for 10 days in patients with COVID-19. If an unavoidable indication appears during patient stay (e.g. autoimmune disease) the patient should be treated. In this case, the study treatment will be stopped to avoid unnecessarily high-dose of hydrocortisone. However, short-duration administration of open corticosteroids will be allowed for prevention of post-extubation laryngeal edema.

- Continuous infusion of neuromuscular blocking agents is to be avoided. In the case it will be indicated (e.g. for severe ARDS), this will be for the shorter period possible and an interruption of the infusion will be planned every 12 hours, to insure not to prolong the treatment longer than necessary.

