7.3 RECORDING AND REPORTING ADVERSE EVENTS

7.3.1 Definitions

According to Article R.1123-46 of the Code de la Santé Publique (French Public Health Code):

Adverse event

Any untoward medical occurrence in a study participant, which does not necessarily have a causal relationship with the study or with the product subject to the study.

Adverse reaction

An adverse event occurring in a study involving human participants when this event is related to the study or to the product being studied.

Adverse reaction to an investigational medicinal product

Any untoward and unwanted reaction to an investigational medication regardless of the dose administered.

• Serious adverse event or reaction

Any adverse event or reaction that results in death, threatens the life of the participant enrolled in the study, requires hospitalisation or prolongs existing hospitalisation, causes a severe or long-term disability or handicap, or results in a congenital abnormality or deformity, and in the case of a medication, regardless of the dose administered.

Unexpected adverse reaction to an investigational medicinal product

Any adverse reaction to the product whose nature, severity, frequency or outcome is inconsistent with the standard safety information described in the summary of the product characteristics, or in the investigator's brochure if the product is not authorised.

According to Article R.1123-46 of the Code de la Santé Publique and the guidelines for sponsors of clinical trials (ANSM):

Emerging safety issue

Any new information that may lead to a reassessment of the risk/benefit ratio of the trial or of the product under investigation, modifications in the investigational medicinal product use, the conduct of the clinical trial or the clinical trial documents, or a suspension, interruption or modification of the clinical trial or of similar trials.

For studies involving the first administration of a health product in healthy volunteers: any serious adverse reaction.

Examples:

a) any clinically significant increase in the frequency of an expected serious adverse reaction;

b) suspected unexpected serious adverse reactions in patients who have terminated their participation in the clinical trial which have been notified to by the investigator to the sponsor, as well as potential followup reports;

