9.2 STATISTICAL METHODS

9.2.1 Adaptive Bayesian analyses

Clinical trial methodology needs to adapt to personalized medicine by including more frequent interim analyses of accumulating data, or by making greater use of those biomarkers information (Saad 2017; Janiaud 2019). An adaptive design is a clinical trial design that allows adaptations or modifications to aspects of the trial after its initiation without undermining the validity of the trial.

Therefore, the aim of the sequential analyses will be to detect treatment-by-biomarker interactions, that is, whether the treatment effect may be different according to biomarkers, that may potentially stop the recruitment of patients presenting with certain levels of that biomarker if there is any evidence that it interacts negatively with the outcome. Treatment effect will be assessed on two main outcome measures, namely a tolerance measure (to detect potential deleterious effects of treatment in some subsets) and an early surrogate efficacy measure (to detect a potential futility to continue treatment evaluation in some cohorts). As described above (section 4.8.2), the tolerance measure will be the occurrence within the first RECORDS" protocol, version 4.0 of 03/03/2021

7, 14 and 28 days of any grade 3 or over adverse events such as hospital-acquired infections, hyperglycemia, hypernatremia, neurological disorders, and the efficacy measure will be the number of vasopressor-free days within the first 28 days.

Search for treatment-by-cohort interactions will be based on each endpoint, and each cohort, separately. Let A and B denote the 2 treatment arms. The treatment effect, 0, of A over B will be considered as the parameter of interest.

Let consider a set of K biomarkers available at baseline, with $x_i = (x_{1i}, \dots, x_{Ki})$ the set of biomarkers for subject *i*, and $Y_{ii} = 1$ the outcome of subject i in arm j.

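### Coma in the safety composite is a bare Glasgow score below 8, so sedation-related or pre-existing low scores may count as safety events

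*Protocol*

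**What the plan says.** Section 5.14.2, item 9, sets a safety endpoint: "Proportion of patients affected by any serious adverse events associated with corticosteroids, among the following", followed by a list that ends with "neurological disorders (coma, stroke or muscle weakness, as defined below) during the 90 days after randomization". The definition referred to is "Coma will be defined as a Glasgow coma score < 8". Sections 7.1 and 7.2 repeat the endpoint and the definition unchanged.

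Section 9.2.1 defines the tolerance measure for the sequential analyses as occurrence within "7, 14 and 28 days of any grade 3 or over adverse events such as hospital-acquired infections, hyperglycemia, hypernatremia, neurological disorders". It does not itself mention coma or a Glasgow threshold. Sections 4.5.1 and 9.2.1 allow recruitment of a biomarker group to stop on evidence of harm.

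On the population and its care, section 4.1.2.1 admits septic shock and "acute respiratory distress syndrome (ARDS Ranieri 2012", with a PEEP requirement. Sections 5.4, 5.12.2 and 5.15 list mechanical ventilation and sedatives among the co-interventions to be recorded. Section 5.12.1 says "Continuous infusion of neuromuscular blocking agents is to be avoided" but provides for its use when indicated.

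**The concern.** In an ICU population of this kind, a low Glasgow score can be a product of care or of the illness at entry. The definition separates neither from a new neurological event after randomisation: it has no condition on sedation or neuromuscular blockade, no comparison with baseline, and no minimum duration. Sedative use is recorded, but nothing links it to the Glasgow score.

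What is at stake is the readability of the safety composite. If sedation-related scores enter equally in both arms, they add events that carry no information on corticosteroid harm. If they enter unequally, they shift the comparison. Sedation happens after randomisation and goes with ventilation, which the treatment may shorten, so balance between arms is not assured. The same applies to the tolerance measure if it takes neurological disorders in the sense of 5.14.2.

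**Working it through.** **What the plan gives.** No rate, sample size or power is stated for coma, for the safety composite or for the tolerance measure, so there is no figure of the plan's own to reproduce on this point. The nearest binary calculation, in 9.1, is 373 per arm for 45% against 35% at 80% power. It does reproduce: (1.96 + 0.8416)² × (0.45×0.55 + 0.35×0.65) / 0.10² = 372.8, so 373. It is used below only as a sample size of the trial's order.

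**Text check.** The definition is identical in 5.14.2 and 7.2. The only Glasgow assessments scheduled by name are at ICU and hospital discharge (5.14.2) and at days 90 and 180 (5.5, 5.15). No section shown tells a site how to class a sedated patient or whether coma must be new.

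**Equal counting in both arms (illustration).** Let p be the true event risk and s the share of patients with a sedation-related or pre-existing score below 8 that is counted, independent of p. The observed risk is s + (1 − s)p, so the risk difference shrinks by the factor (1 − s). Assumed values: p = 20% and 30%, 373 per arm, two-sided 5% test of two proportions.

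| s | Observed risks | Difference | Power |
|---|---|---|---|
| 0 | 20.0% vs 30.0% | 10.0 points | 88.5% |
| 0.3 | 44.0% vs 51.0% | 7.0 points | 48.2% |
| 0.5 | 60.0% vs 65.0% | 5.0 points | 29.1% |
| 0.7 | 76.0% vs 79.0% | 3.0 points | 16.4% |

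**Unequal counting between arms.** Keep true risks of 20% (placebo) and 30% (corticosteroid).
- With s = 0.50 on placebo, the observed placebo risk is 0.50 + 0.50×0.20 = 60%.
- With s = 0.43 on corticosteroid, the observed risk is 0.43 + 0.57×0.30 = 60.1%. A 10-point excess of harm has all but vanished.
- In the other direction, take no true difference (20% in both arms) and s = 0.57 on corticosteroid: 0.57 + 0.43×0.20 = 65.6% against 60%, an apparent harm of 5.6 points.

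**The actual adaptive criterion.** Section 9.2.1 does not test arm against arm. It uses the posterior probability that a ratio of standardised effects, subset over remainder, exceeds a threshold. Assume true risks of 35% vs 20% in the subset and 25% vs 20% in the remainder, and take the denominator as the square root of p̄(1 − p̄):
- s = 0 in both: 0.336 / 0.120 = 2.81.
- s = 0.3, 0.5 or 0.7 in both: 2.99, 3.04, 3.07. The point value hardly moves, and the loss is precision.
- s = 0.7 in the subset and 0.3 in the remainder: 0.109 / 0.070 = 1.55.
- s = 0.3 in the subset and 0.7 in the remainder: 0.210 / 0.036 = 5.92 before rounding.

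Without the square root the pattern is the same: 2.62 with none counted; 2.98 to 3.15 with equal s; 1.88 and 5.00 with unequal s.

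**The case against.** A reader might infer that every sedated, ventilated patient is counted as harmed. The documents do not support that. The composite is worded as serious adverse events associated with corticosteroids, section 7.3.1 starts the definition of an adverse event from "Any untoward medical occurrence in a study participant", and 7.3.2 has the investigator assess seriousness, intensity and, for serious events, causality. Intended sedation need not pass these filters. This part of the objection stands: counting is the literal reading of the definition, not a certainty. But the protocol does not say that the filters exclude such scores, so sites may class the same patient differently.

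A reader might also infer that the bare definition drives cohort closure. Section 9.2.1 names only neurological disorders and requires grade 3 or over, so the link to 5.14.2 is plausible but inferred.

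Nor can a fall in power between arms, such as that in the first table, be taken as the operating characteristic of the adaptive rule. That rule is a ratio between subsets, where equal contamination mainly costs precision. Dilution is therefore only one possible outcome; unequal contamination gives bias.

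Finally, scoring under sedation might be handled in the Glasgow addendum (15.4.5), which is listed but not reproduced, or in the statistical analysis plan. That is possible. But the protocol fixes this definition itself, twice, and a later plan cannot recover a pre-sedation score or sedation status at scoring if sites did not record it.

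**Conclusion.** The point holds as a weak definition. Coma in sections 5.14.2 and 7.2 is a Glasgow score below 8 with no condition on sedation, neuromuscular blockade or new onset, in a population for which ventilation and sedatives are expected. Low scores that are sedation-related or pre-existing may therefore enter the 90-day safety composite, and also the tolerance measure if that uses the same definition.

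The effect is added noise if such scores are balanced, and bias in either direction if they differ by arm or biomarker subset. Its size cannot be derived from the documents. The figures above rest on assumed event risks, an assumed counted share, independence of that share from true harm, and, for the power figures, a borrowed sample size. They show direction and mechanism, not an expected loss. The point concerns a secondary safety endpoint and possibly the tolerance rule; it does not touch the primary outcome.

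**What to change.** In 5.14.2 and 7.2, define coma for the safety composite as a Glasgow score below 8 that is new since randomisation (baseline 8 or more, using the last pre-sedation score if the patient is sedated at entry) and that was not scored under sedation or neuromuscular blockade. State in 9.2.1 that the tolerance measure uses the same definition. Add an eCRF field for sedation status at the time of scoring.

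Leave the list in 7.3.2.2 unchanged. It names coma without a qualifier and covers events that would not be classed as serious; narrowing a notification trigger is a separate safety trade-off and is not needed for the analysis.

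The cost is wording in three sections and one data field. The downside is fewer coma events. Coma in patients who die while sedated would not be counted in the composite, which does not list death as a component, although their deaths are counted in the mortality outcomes.
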